1	Official Title: "Does Intravenous Lactated Ringer's Solution Raise
2	Serum Lactate?"
3	
4	NCT number: NCT02950753
5	
6	Date approved by IRB: Nov 17, 2016
7	
8	
9	
10	
11	
12	
13	
14	
15	
16	
17	
18	
19	
20	
21	
22	
23	

24 Introduction

26	Since "early goal-directed therapy," early recognition of septic shock using the serum
27	lactate has become standard of care [1-4]. Indeed, the central place of lactate in sepsis
28	care has been promoted by the Surviving Sepsis campaign, and it is now backed by
29	financial incentives for hospitals with its adoption as a CMS Core Measure [5].
30	
31	In this context, it is important to elucidate all possible causes of hyperlactatemia.
32	Previous studies have shown that serum lactate increases in all shock states, not just
33	septic shock [6]. Furthermore, lactate has also been shown to increase from albuterol [7],
34	anti-retroviral medications, metformin, propofol, and alcohols [8].
35	
36	According to Surviving Sepsis Guidelines, patients diagnosed with septic shock should
37	receive 30 mL/kg of crystalloid solution within three hours [9]. One commonly used
38	crystalloid, Lactated Ringer's solution (LR), contains 28 mmol/L of racemic lactate in the
39	form of sodium lactate. While lactate is rapidly metabolized by the liver and kidney,
40	aggressive fluid resuscitation with LR may transiently raise serum lactate, potentially
41	confounding the interpretation of this test.
42	
43	There has only been one trial looking at the question of whether administration of LR
44	raises serum lactate. That study did not show a difference in lactate levels in those
45	receiving LR versus those receiving alternative crystalloid solutions. However, that study
46	used only 1 liter of LR delivered over one hour [10]. As mentioned above, patients in

47	septic shock are mandated to receive 30 mL/kg of crystalloid solution, and the fluids are	
48	typically given at a rate faster than 1 liter per hour. Therefore, when LR is given at a	
49	volume and rate more similar to what is done for septic shock patients, LR may have an	
50	effect on serum lactate level that was not identified in the previous study.	
51		
52	Thus, we propose a double-blind, randomized controlled trial to investigate whether the	
53	administration of intravenous LR at 30 mL/kg increases levels of serum lactate. As our	
54	study compares the effect of NS and LR, it lends itself easily to secondarily investigating	
55	changes in sodium (Na), chloride (Cl), and pH in the NS group compared to the LR	
56	group.	
57		
58	Materials and Methods	
59		
60	Study Design and Setting	
61		
62	This will be a double-blind, randomized controlled trial performed on a group of healthy	
63	volunteers, made up primarily of family, friends, and colleagues of the investigators.	
64		
65	All subjects will be healthy volunteers aged 18 years or older. Healthy volunteers are	
66	defined as subjects with no acute symptoms who meet none of the following exclusion	
67	criteria: pregnant, breast-feeding, prisoners, history of conditions associated with fluid	
68	overload (congestive heart, renal, or hepatic failure), baseline serum lactate level >2.2	
69	mmol, and baseline creatinine >1.5 mg/dL.	

7	Λ
1	υ

71 All volunteers will fill out a short data collection form assessing their age, weight, 72 gender, and medical history. All volunteers will signed a written consent, approved by the 73 IRB. 74 75 A random-number generator will be used to assign each subject to either LR or NS. After 76 assignment, a pharmacist with no role in data collection prepared the fluids in a locked 77 room. The pharmacist will use an opaque black bag to obscure the fluids. The subjects 78 will then receive 30 mL/kg rounded to the nearest 100 mL of the solution to which they 79 were randomized. 80 81 An investigator will place an 18 gauge IV in one upper extremity, and an initial serum 82 lactate and electrolyte panel will be drawn, measured using the i-STAT 1 analyzer 83 (Abbott Point of Care, Princeton, NJ). Fluids will be administered as a rapid bolus via 84 pressure bag. Post-treatment blood will be drawn from the contralateral upper extremity 85 five minutes after the conclusion of the IV fluid administration. 86 87 Outcomes 88 89 The primary outcome will be the difference in change in serum lactate levels between the 90 LR and NS groups. Secondarily, we will compare the change in lactate within each group 91 (before and after treatment), and we will compare the change in pH, creatinine, 92 bicarbonate, Na, and Cl levels between NS and LR groups.

93

94 Data Analysis

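### Eligibility and the data form leave out recent albuterol and alcohol, which the Introduction lists as raising lactate; this costs precision and weakens the within-group tests

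*Combined protocol and SAP*

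**What the plan says.** The Introduction states that "lactate has also been shown to increase from albuterol [7"] and extends the list to "anti-retroviral medications, metformin, propofol, and alcohols [8"].

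Study Design and Setting makes eligible any adult healthy volunteer, "defined as subjects with no acute symptoms who meet none of the following exclusion" criteria. These are "criteria: pregnant, breast-feeding, prisoners, history of conditions associated with fluid" "overload (congestive heart, renal, or hepatic failure), baseline serum lactate level >2.2" mmol, and "baseline creatinine >1.5 mg/dL". None concerns a medicine, alcohol, a washout or a period of abstinence.

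The same section describes the baseline form: "All volunteers will fill out a short data collection form assessing their age, weight", "gender, and medical history". Current medicines and recent intake are not named.

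Under Outcomes, the primary outcome is the between-arm difference in lactate change. The change runs from the baseline draw to a draw five minutes after the bolus ends. Before-after change within each arm is secondary. Data Analysis plans an unadjusted two-tailed t-test for the former and paired t-tests for the latter.

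**The concern.** The trial is meant to isolate one cause of a raised lactate. It names other causes and then neither screens for them nor, on the description given, records them. A symptom-free volunteer who used albuterol or drank alcohol shortly before the visit is eligible as written.

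The baseline cap of 2.2 does not close the gap. It is a single reading of the level, while the outcome is what happens after that reading. A volunteer may pass the cap with lactate still rising after albuterol, or pass at 2.0 after alcohol and then fall.

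Two things are at stake: the precision of a small primary comparison, and the meaning of the before-after tests, which cannot separate such drift from an effect of the fluid.

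**Working it through.** **Inputs from Data Analysis.** Sample size 30, difference 0.5 mmol/L, SD of the change 0.5, alpha 0.05 two-sided, power 80%. Assumed, because not stated: 30 is the total and is split 15 and 15.

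**The plan's own figure.**
- Normal approximation: n per arm = 2 × (1.960 + 0.842)² × (0.5/0.5)² = 15.7, so 16 per arm or 32 in all.
- At 15 per arm the standard error of the difference is 0.5 × √(2/15) = 0.183. Power is Φ(0.5/0.183 − 1.960) = 78.2%. The stated 80% with 30 is reproduced approximately.
- The noncentral t (28 df), which matches the planned test, gives 75.3%. This is the baseline used below.

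**Effect of drift on the primary comparison.** Let a share p of subjects carry an extra change s unrelated to the fluid. The documents give neither, so both are assumptions. The SD becomes √(0.25 + p(1 − p)s²).

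| p | s (mmol/L) | SD | Power, 15 per arm |
|---|---|---|---|
| any | 0 | 0.500 | 75.3% |
| 2 of 30 | 0.5 | 0.515 | 72.7% |
| 3 of 30 (10%) | 0.5 | √0.2725 = 0.522 | 71.6% |
| 2 of 30 | 1.0 | 0.559 | 65.8% |
| 3 of 30 (10%) | 1.0 | √0.34 = 0.583 | 62.1% |

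If 30 is per arm, 10% drifting by 1.0 mmol/L lowers power from 96.8% to 90.4%.

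**Bias and type I error.** In simulation of the t-test (40,000 trials per setting; 2, 4 or 6 exposed of 30; s = 0.5 or 1.0; exposure independent of arm), the mean estimate stayed at 0.50 and type I error at about 5%. Only power fell.

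**Chance imbalance in one trial.** With two exposed subjects, both fall in the same arm with probability 2 × (15 × 14)/(30 × 29) = 48.3%, in either direction equally often. The estimate then shifts by 2 × 0.5/15 = 0.07 mmol/L at s = 0.5, or 2 × 1.0/15 = 0.13 at s = 1.0. The larger shift is 0.13/0.183, about 0.7 of a standard error.

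**Within-group tests.** Take 15 NS subjects, no true fluid effect, SD 0.5, and a paired t-test at 5%. Simulated false-positive rates are about 5% with one subject drifting by +1.0 mmol/L, about 8% with two, and about 14% with three. With three drifting by +0.5 the rate is about 8 to 9%. Here the drift is not noise around zero: it moves the mean change by k × s/15, for example 3 × 1.0/15 = 0.20 mmol/L.

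**The case against.** The strongest reply is that the design already protects the main result. There is a concurrent blinded NS arm, a change-from-baseline outcome, a cap that removes clearly raised entrants, and only one rapid bolus plus five minutes in which lactate can drift. This stands for the primary comparison. A reader might infer that the LR-versus-NS estimate is biased; it is not, on average, and the t-test already allows for the imbalance computed above.

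A reader might also infer that every listed agent contaminates the change score. That goes too far. A steady elevation from constant metformin or anti-retroviral use cancels when baseline is subtracted. Only lactate that moves between the draws counts, which points chiefly to recent albuterol and alcohol.

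The power figures rest on assumed inputs. The fall to 62% needs 10% of subjects to drift in the same direction by 1.0 mmol/L, twice the difference the trial calls clinically significant. Albuterol and alcohol may also act in opposite directions. The SD of 0.5 has no stated source, so it may already include some of this variation, and adding more could count it twice.

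Nor do the documents show that exposed subjects could never be identified. Medical history is recorded and might reveal asthma, diabetes or HIV, and the form itself is not reproduced. Medical history would not, however, show what was taken before the visit.

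The reply does not reach the within-group tests, which have no control arm.

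**Conclusion.** The point holds as a modest gap in precision and recording, and does not invalidate the primary comparison. The eligibility list admits people recently exposed to agents that the protocol itself says raise lactate, and the form as described would not show who they were.

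The cost ranges from nothing, if no such volunteer enrols or their lactate is stable, through about 4 points of power at 10% and 0.5 mmol/L, to about 13 points at 10% and 1.0 mmol/L. These figures assume 15 per arm and an SD of 0.5 that does not already contain the drift. The documents do not show which part of that range applies. The before-after tests are the more exposed: two or three of 15 subjects drifting by 1.0 mmol/L raise a nominal 5% error rate to about 8 to 14%. The change is worth making because it is nearly free and because intake not recorded before the draw may not be recoverable later.

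**What to change.** 1. In Study Design and Setting, add an exclusion, or a rebooking rule, for recent use of albuterol or another beta-agonist and for recent alcohol before the baseline draw. The documents give no basis for a particular window, so the sponsor should set and justify it.
2. Add current medicines and recent intake to the existing form, and check the answers before the baseline draw.
3. State whether volunteers on stable metformin or anti-retroviral treatment are eligible. Recording such use is enough for the change score; exclusion is not required by the argument here.
4. In Data Analysis, prespecify a sensitivity analysis of the primary and within-group comparisons that omits users of any agent the Introduction lists.

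The cost is one eligibility sentence, two form questions and one extra analysis, with no new procedure or staff. A few volunteers may be rebooked or excluded, and the population becomes slightly narrower, which matters little in a mechanistic study of healthy people.
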